[name] (PI) will provide guidance for overall study policy development, achievement of scientific aims, data analysis, publication and quality assurance for the study. [name] will oversee the implementation of the aims of the study and maintain communication across both sites. Policy guidelines for the project and quality assurance include standards for staff training, assessment, treatment, quality control and maintenance procedures, as well as data review and analysis. Assessment and Intervention Manuals and Manual of Operations will be created in Miami and adapted to the Zambian context through consensus by both teams. “Like Father, Like Son” intervention manuals and assessments will be collaboratively developed by US and Zambia investigators with input from stakeholders. Publications and authorship will be collaboratively developed and shared between both sites.

Decisions on procedural issues and scientific management will be reached using a Project Executive Committee, chaired by [name], comprised of Drs. [name], [name], [name], [name], [name], and [name]. During semi-annual meetings, [name] and [name] will provide additional consultation on the project, providing guidance on the current standards on EIMC/VMMC and information on regional EIMC/VMMC uptake and acceptability. [name] will oversee quality assurance and training and chair the Publications Committee; [name] will oversee statistical issues and data review. The committee will meet twice a year in person during site visits, and twice per month on conference calls.

[name] (co-PI) will chair the Project Steering Committee, comprised of [name], [name], [name], and [name], and oversee the scientific/operational arms of the study, and be responsible for site-specific program management, e.g., administration and site issues that may impinge on study conduct and/or outcome and operating procedures. [name] will also organize and oversee the training of qualified healthcare providers from the 8 CHCs to perform VMMC and EIMC at the University Teaching Hospital. Decisions on procedures for recruitment, intake, assessment, treatment, maintenance and follow-up will be reached by the Project Steering Committee. The Committee will meet weekly, and minutes will be provided to the Miami site as a record of study progress.

[name] (co-Investigator) will oversee all administrative issues related to the project, including procedures for deployment of staff to clinics, behavioral training, and clinic

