Women and VMMC. Men participating in S&S were encouraged to invite their female partners to participate, as the national Zambia Sexual Behaviour Survey found men viewed their partners' potential preference for an uncircumcised penis as an impediment to considering VMMC (Central Statistical Office, MOH, University of Zambia, and MEASURE Evaluation, 2010). The S&S intervention, with female participation of 80%, found a 6% increase in uptake of VMMC among Experimental participants attributable to positive shifts in women's preferences (see Preliminary Studies, Cook et al., 2015). To optimize women's influence on VMMC decision-making, the comparable women's intervention focused on VMMC attitudes and beliefs and highlighted VMMC health benefits for women (Westercamp et al., 2012; Lanham et al., 2012).

Early Infant Male Circumcision (EIMC, performed during the first 60 days of life). EIMC is a safer, simpler and less expensive procedure with shorter healing times than adult VMMC ([name] et al., 2010; Binagwaho 2010; WHO/UNAIDS 2007). In addition to offering lifetime protection from several disorders/diseases, EIMC is associated with improved penile hygiene and fewer of the urinary tract infections (UTIs) that are prevalent in uncircumcised infants. By increasing the availability and acceptability of both EIMC and VMMC, the overall population health benefit of male circumcision could be realized in less than one generation. Consequently, as VMMC promotion began, the Ministry of Health began development of an EIMC program as a longterm HIV prevention solution for the ~360,000 male neonates born yearly in Zambia (GRZ Central Statistics Office, 2018). However, a study by Waters et al (2013) of 2000 Zambian pregnant women provided with information on EIMC, found although 97% agreed they would circumcise their infant if they had a boy, only 11% actually did so. More recently, the Zambia Operational Plan for VMMC 2016-2020 (RZMOH, 2016) reported that significantly lower uptake of infant MC had been achieved than originally targeted. In fact, as of October 1, only 1,181 of the 362,078 newborn males in 2018 underwent EIMC (GRZ Central Statistics Office, 2018; clinic data); in EIMC trained clinics in Lusaka, only ~0.02% of male infants were circumcised in 2018 (clinic data).

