Little research has evaluated the impact of demand creation on EIMC uptake. However, studies that evaluated uptake in response to information on EIMC (Waters et al., 2013; Mavhu et al., 2015; Mavhu et al., 2016; Kankaka et al., 2017; Plank et al., 2013) found EIMC uptake did not reflect reported acceptability. This discrepancy between theoretical acceptability and actual uptake has not been addressed. Barriers to EIMC suggest that poor uptake may arise from the bottleneck created by the final decision resting with husbands; 85% of women indicated that husbands' agreement is important, and only 10% of women identified as sole decision makers (Albert et al., 2011). Parents were more willing to accept EIMC if fathers were circumcised, if mothers were more educated, if couples were serodiscordant, or if parents were aware of the benefits of EIMC (Waters et al., 2013; Mugwanya et al., 2011; Young et al., 2016). While 83% of mothers in South Africa accepted EIMC, many refused the procedure as they were required to first discuss it with their husband and/or family (Young et al., 2016). Decisions governing sons are traditionally the purview of the father in most African societies, although the opinions of mothers and paternal family members may also be solicited (Mavhu et al., 2017). In addition, studies suggest that fathers "need to be provided with information directly, not just through their wives" (Mavhu et al., 2017; GRZ 2018). The proposed study will attempt to bridge the gap between hypothetical acceptability and low uptake by creating an intervention to increase acceptability and availability of EIMC and VMMC during the perinatal period, focusing on both parents and the option of a shared father-son circumcision experience. As such, pregnancy provides a "window of opportunity" to encourage the participation of both members of the couple in a culturally tailored informational/motivational HIV prevention program.

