Participants will meet with study staff and will be verbally screened for eligibility based on the following criteria, by study staff at each clinic.

CAB participants: CABs operate in each CHC clinic and are comprised of community zone leaders in the clinic catchment area; as zone leaders, they educate their community on the study objectives and sensitize their community on study goals, risks and benefits. Eligible CAB members will be men and women aged >18, representing a ward within each experimental CHC site catchment area. Twenty Community Advisory Board (CAB) member participants will be recruited from CABs at each clinic (20 CAB members x 4 clinics, n = 80), and each attendee will be compensated ~\$US10 per visit.

Focus Group participants. Stakeholder participants will be recruited from ANCs to attend gender specific focus group discussions (FGDs). A total of 8 pregnant couples from each of the 4 experimental CHC clinics (8 couples per clinic) will be recruited for this study [2 gender specific FGDs per clinic; (8 men and 8 women) x 4 clinics = 64 participants]. Both members of each couple must enroll to participate. Eligible participants will be pregnant couples (men and pregnant female partners) aged >18, attending the antenatal clinic of the experimental CHC. No personal, individually identifying information will be collected and no individual interviews or assessments will be conducted with FGD Members. Each attendee will be compensated ~\$US10 per visit.

IRB Study Number:

Version #, Date:

S&S+LFLS Participants. Pregnant couple participants (300 couples, n = 600 participants) will be recruited over 18 months via referral from ANC/VCT and enrolled as couples. A total of 75 pregnant couples will be recruited from each of the 4 clinics participating in LFLS (75 pregnant couples per clinic x 4 clinics = 300 couples = 600 individual men and women.) Both members of each couple must enroll to participate. Eligible women will be pregnant (up to 6 months pregnant), aged >18, any HIV status, and the partner of a male participant enrolling (neonates undergoing EIMC are receiving a clinical service approved by parents; only parents are study participants). Eligible men will be aged > 18, any HIV status [in accordance with Zambian and WHO/UNAIDS (2016) policy for MC eligibility], and the partner of the pregnant female participant enrolling. There is no upper age limit for participation, and each person will be compensated ~\$US10 per visit.

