H2. Assess factors relevant to the LFLS model. To investigate the indirect effects of the five main predictors (paternal grandparents' circumcision attitudes, peer attitudes surrounding circumcision, father's HIV status, father's circumcision status, and mother's HIV status) on infant circumcision, a path analysis (Kline, 2011) will be conducted. To estimate the indirect effects, it will be specified that the paths between the five main predictors on infant circumcision will act through father's circumcision attitudes. Mother's circumcision attitudes will be regressed on mother's HIV status, and a regression path between father's and mother's attitudes toward circumcision will be specified. When estimating the indirect effects, results will be adjusted for the effect of number of siblings circumcised.

All potential indirect effects will be estimated by a bootstrapping approach (MacKinnon et al., 2007). R-square of indirect effects will be used as measures of effect size (Fairchild et al., 2009). A sandwich estimator will be used to account for the nested data structure (e.g., individuals are nested by clinics). This estimator uses the Huber/White correction and adjusts for potential underestimated standard errors and bias in chi-square computation (Liang & Zeger 1986).

Missing data will be handled using Full Information Maximum Likelihood estimation procedures (Enders & Bandalos 2001). For model fit evaluations, we will use well-established fit indices and cutoff values: A well-fitting model ideally will have a non-significant model χ^2 , a Comparative Fit Index / Tucker-Lewis Index greater than .95, a root mean square error of approximation less than .08, and a standardized root mean square residual less than .08 (Hooper et al., 2008). All analyses will be conducted in Mplus (V8; Muthén & Muthén, 2017).

H3. Effect of S&S + LFLS pilot. To compare the proportion of EIMCs in the experimental group to the proportion found in the observation group, a one-sample z-test will be conducted. The population proportion will be taken to be the midpoint of the findings from Waters et al. (2013) on neonatal circumcision and historical numbers of circumcisions from Zambian clinics and hospitals. Based upon this rationale, the percentage of EIMCs in the observation group is anticipated to be approximately 5.0%.

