Exploratory analyses. To investigate change in EIMC attitudes, Stages of Change scores will be examined over time using an autoregressive modeling approach specifying the individual's stage at 1-week postpartum as the main outcome and individual's stage at baseline as a main predictor in the regression model (Hamaker et al., 2015). Variables from the previous path model will be included as potential covariates in attempting to explain stage movement. The estimated regression coefficient will reflect changes in EIMC attitudes over time. The model will use an ordinal logistic model to examine change over time. Odd ratios will be estimated as a measure of effect size (Chen et al., 2010).

Power. Using a two-tailed Z test to test the difference in proportions between two conditions at an α level of .05, this study has over 80% power to detect a difference of 6.0% in EIMC rate between the two conditions. This difference in proportion translates to an effect size of an odds ratio (OR) = 2.4, which is considered a small (OR = 1.68) to medium (OD = 3.47) effect size, according to Chen et al. (2010). This 2.4 OR is based on an effect size found in previous research examining circumcisions ([name] et al., 2015). With these specified parameters, 80% power is achieved with 140 couples (out of ~151 couples with male infants).

Data Security. CAB and FGD participants will not provide any uniquely identifying information during participation in group discussion sessions. Pregnant couple participants in the intervention will be assigned a unique code upon entering the study. This number will identify all participant files, which will include no identifiable information. Access to the computer data files will be restricted by password codes. The list translating participant number to identifying information

IRB Study Number:

Version #, Date:

will be maintained in a secure locked file in the Spear & Shield study office in Lusaka at the University of Zambia School of Medicine. Participants will be made explicitly aware at the time of the informed consent of the nature of the separate record that will be kept for them. CAB and focus group discussions will be audio-taped for review and summary of key discussion points; copies will be stored in a locked cabinet at the PI's Lusaka offices, and deleted following summarization.

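### The H3 test sets interested, jointly enrolled couples against a 5% reference that describes neither of its two sources, so a positive result cannot separate a programme effect from information plus selection

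*Combined protocol and SAP*

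**What the plan says.** **Who is analysed.** Section 7 has clinic staff brief potential candidates and refer those who show interest. For the intervention couples it states: "Both members of each couple must enroll to participate. Eligible women will be pregnant (up to 6 months pregnant), aged >18, any HIV status". Observation clinics recruit nobody and supply aggregate counts only (section 12, Design).

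**What they are tested against.** Section 14 (H3) specifies a one-sample z-test. The fixed proportion is the midpoint of an earlier Zambian study and historical clinic and hospital numbers, and the plan concludes that "the percentage of EIMCs in the observation group is anticipated to be approximately 5.0"%.

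**The two sources.** Section 6 reports that the earlier study, in 2000 Zambian pregnant women given EIMC information, "found although 97% agreed they would circumcise their infant if they had a boy, only 11% actually did so". For historical uptake it gives 1,181 of 362,078 male newborns nationally in 2018 and about 0.02% in EIMC-trained Lusaka clinics.

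**Power.** Section 14 (Power) assumes a two-sided test at the 5% level and claims that "this study has over 80% power to detect a difference of 6.0% in EIMC rate between the two conditions". On the size of the effect it says: "This difference in proportion translates to an effect size of an odds ratio (OR) = 2.4". On the sample it says that "80% power is achieved with 140 couples (out of ~151 couples with male infants").

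**The concern.** The reference averages two very different groups and describes neither. Couples who were interested, and in which both partners enrolled, need not behave like all male births in a facility or a country. Section 6 gives a reason to expect a difference: it treats the father's decision as the bottleneck and reports that "85% of women indicated that husbands' agreement is important, and only 10% of women identified as sole decision makers". Enrolling the father may therefore select couples more open to EIMC.

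The powered target of 11% is also the uptake already reported after pregnant women received EIMC information. Section 6 says that studies of uptake after information found it fell short of stated acceptability, and that this study will try to bridge the gap. H3 could be positive at, or somewhat below, a rate that section 6 presents as disappointing.

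What is at stake is the reading of the pilot. If it succeeds, the team intends to plan a clinical trial (section 12), and the timeline in section 10 ends with a grant application.

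**Working it through.** **Inputs**
- Reference p0 = 0.05 (section 14, H3).
- Two-sided α = 0.05, difference 0.06, n = 140 (section 14, Power), so p1 = 0.05 + 0.06 = 0.11.
- Source rates 11%, 1,181/362,078 = 0.33%, and about 0.02% (section 6).
- Outcomes treated as independent, as the plan's test does.

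**1. The plan's own figure.** Odds ratio: (0.11/0.89)/(0.05/0.95) = 2.35, consistent with the stated 2.4. One-sample power:

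Φ{[(p1 − p0)√n − 1.96√(p0(1 − p0))]/√(p1(1 − p1))} = Φ{[0.710 − 0.427]/0.313} = Φ(0.904) = 81.7%.

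The stated power reproduces, so the arithmetic is not at fault.

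**2. The midpoint.** (11 + 0.33)/2 = 5.66% and (11 + 0.02)/2 = 5.51%. The stated 5.0% is slightly below both.

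**3. Smallest significant count against 5%.** 0.05 + 1.96√(0.05 × 0.95/140) = 0.0861, and 0.0861 × 140 = 12.05. So 13 of 140 (9.3%) is needed, a rate below 11%.

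**4. Chance of a positive test by true rate.** P(X ≥ 13) = 1 − Σ(k = 0 to 12) C(140, k) p^k (1 − p)^(140 − k).

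| True rate in enrolled couples | P(X ≥ 13) | Source of the rate |
|---|---|---|
| 5% | 2.4% | plan's reference |
| 7% | 18% | assumption |
| 8% | 33% | assumption |
| 9% | 50% | assumption |
| 11% | 78% | section 6; also the powered alternative |

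With a reference of 5.5% to 5.7% the critical count is 13 or 14, and the chance at a true 11% is still about 69% to 78%.

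**5. The same data beside 11%.** 0.11 + 1.96√(0.11 × 0.89/140) = 0.1618, and 0.1618 × 140 = 22.66. So 23 of 140 (16.4%) is needed. The exact probability of 23 or more is:
- 3.3% at a true 11%
- 61% at a true 17% (60% by the normal formula)
- 81% at a true 19%.

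**6. What an interval would show.** The Wilson 95% interval is [p + z²/2n ± z√(p(1 − p)/n + z²/4n²)]/(1 + z²/n). With p = 13/140 and z = 1.96 it runs from 5.5% to 15.2%. It excludes 5% and includes 11%, which the planned test alone would not reveal.

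**The case against.** The strongest reply is that the plan asks a different question. H3 as worded compares programme clinics with clinics that receive procedure training only. Information is part of the programme, so any gain it produces belongs to the programme's effect. Against the roughly 0.02% reported for trained Lusaka clinics, 5% is a demanding bar. This stands as a reason not to make 11% the sole reference. It does not rescue the test: no specified analysis uses the observation clinics' counts, and nothing in the plan removes the selection of couples.

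A reader might also infer stronger things that the documents do not support:

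- *That the eligibility rule is wrong.* Enrolling both partners is integral to a couples' intervention, and section 6 argues that fathers need information directly. No criterion asks about interest in EIMC, and consent to a paid study is not agreement to circumcision. That the rule screens out opposed fathers is plausible but unmeasured.
- *That the 11% group is a proper match.* Section 6 calls them pregnant women given information. It does not state where they were recruited, whether partners took part, or whether 11% is of all women or only of mothers of boys.
- *That 78% is a false-positive rate.* It is essentially the plan's own power. It becomes an error rate only if these couples would reach 11% without the programme, which is unknown.
- *That the trial would recommend the programme.* The documents call it an exploratory feasibility pilot that may lead to a further trial.

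**Conclusion.** The concern holds as a defect in the H3 reference and in what a positive result would be taken to mean. A significant result can occur from 9.3% upward, and is about 78% likely at a true 11%, the rate already reported after information. It would therefore not distinguish a programme effect from information plus selection.

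The critical counts and the 78% follow from the plan's figures, assuming independent outcomes. The 18% to 50% range rests on assumed underlying rates of 7% to 9% that appear nowhere in the documents. The size of any selection effect cannot be derived from them, but the interpretive problem does not depend on knowing it.

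**What to change.** In section 14 (H3):

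1. Report uptake among enrolled couples with male infants, with its 95% confidence interval, against both 5% and 11%, and explain how each figure was obtained.
2. State in advance that exceeding 5% but not 11% will not be interpreted as an effect of S&S+LFLS beyond information and selection.
3. Keep historical facility and national rates for clinic-level counts only. Specify an assessment of H3 as worded, experimental versus observation clinics, using the monthly EIMC counts and the 12 months of history already collected at all 8 clinics.
4. Tabulate uptake by baseline EIMC Stage of Change, already among the planned assessments, so that couples leaning towards EIMC at entry are visible.

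The cost is analysis-plan wording, one specified clinic-level comparison and one table; no extra participants or visits. The drawback is a less favourable claim. Against 11%, at least 23 of 140 (16.4%) is needed, a true 17% has only about 60% power, and about 80% power needs a true rate near 19%.

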Protocol development Identify 8 Lusaka CHCs Clinic sensitization Historical (1yr) data collection Monthly VMMC/EIMC data collect CAB meetings, FGDs, interviews Feedback & Prepare LFLS	X X X X X	X X X X X		X X	X	X X	X X	X X		X X		
Train 2 Providers at all 8 sites in EIMC/VMMC (n=16) Train 2 Providers (n = 8) at the 4 Experimental sites in S&S+LFLS		X X										
Experimental: Recruit & Assess n=300 Pregnant Couples			X X	X X	X	X X	X X	X X				
Provide VMMC/EIMC Services Prenatal: S&S+LFLS Session 1			X X	X X	X X	X X	X X	X X				
Postpartum: LFLS Session 2 Postpartum Follow-up Assess				X X	X X	X X	X X	X X	X X			
6 mos post-partum: Assess EIMC/VMMC (father, sons, infant)						X	X	X	X	X		
Data Analysis. Manuscripts. Prepare R01 application											X	X

Community Advisory Board (CAB) Members. CAB Members will meet for three formal group discussions in a private meeting room within their experimental clinic. CAB members will be asked to 1) provide input on cultural factors that influence attitudes, perceptions, and beliefs about EIMC within their communities and among the ethnic groups predominant in the Lusaka Province, and 2) provide input on the LFLS intervention and assessment content and information on community issues and concerns that could influence LFLS program uptake. CAB Members associated with each CHC will thereby facilitate the adaptation of the intervention strategies to the local culture and clinic culture, enabling LFLS to work with the community rather than imposing the program on the community. No personal, individually identifying information will be

IRB Study Number:

Version #, Date:

collected and no individual interviews or assessments will be conducted with CAB Members.

Focus Group Discussion (FGD) Members. FGD members will meet in gender concordant groups in a private room within their experimental clinic site; members will provide input on cultural factors that influence attitudes, perceptions, and beliefs about EIMC among pregnant couples. They will provide guidance on cultural attitudes, ethnic preferences, beliefs and perceptions surrounding EIMC among pregnant couples in Lusaka. FGD members will inform the study on local issues or community concerns that could influence program uptake. No personal, individually identifying information will be collected and no individual interviews or assessments will be conducted with FGD members.

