Pregnant Couple Members attending LFLS. All S&S+LFLS study participants will be followed from enrollment to six months post-partum (maximum ~ time of participation based on enrollment at ~3-4 months pregnant = 12 months). Participants will complete baseline, pre-and post-partum and 6-months post-partum assessments and attend the Spear & Shield and 2 LFLS intervention sessions (see below).

Enrollment will be conducted from month 7 – 24, a total of 18 months.

11) **Study Endpoints***

Primary and secondary study endpoints.

Primary endpoints.

- EIMC uptake (infant)
- VMMC uptake (father and other sons)

Secondary endpoints.

- Father's and mother's circumcision attitudes

Primary or secondary safety endpoints.

This is a behavioral feasibility study, not requiring safety endpoints.

12) **Procedures Involved***

Design.

Like Father Like Son(s) proposes to develop intervention materials and test the effectiveness of the intervention to enhance the uptake of early infant male circumcision (EIMC) and voluntary medical male circumcision (VMMC) in the community health center (CHC) setting.

The study utilizes a longitudinal repeated measures design [2 (condition) x 4 (time points)]. The pilot study intervention will expand the Spear & Shield (S&S) intervention to include the “Like Father Like Son” component (S&S + LFLS).

IRB Study Number:

Version #, Date:

The pilot study will randomize 8 clinics to Experimental and Observation conditions; clinics will be matched on catchment area size and current EIMC and VMMC rates.

Experimental clinics (n = 4) will be trained to offer “S&S+LFLS”; Observation clinics (n = 4) will be “Observation Only” sites. Observation only sites will not recruit participants and will only be “observed” regarding the total number of VMMCs and EIMCs conducted at each individual clinic - Observation Only clinics will only provide clinic level aggregate data.

The study will train both Experimental and Observation Only clinic staff to conduct VMMC and EIMC procedures in order to provide equivalent services at all clinics, controlling for the availability of circumcision at all sites. Participants will only be recruited from experimental sites. The study will also assess the feasibility and acceptability of offering S&S+LFLS at the CHC level, and if successful, plan for a clinical trial of the S&S+LFLS intervention.

CAB Meetings & Focus Groups.

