CAB Members associated with each CHC will thereby facilitate the adaptation of the intervention strategies to the local culture and clinic culture, enabling LFLS to work with the community rather than imposing the program on the community.

No personal, individually identifying information will be collected and no individual interviews or assessments will be conducted with CAB Members.

Focus Group Discussion (FGD) Members. FGD members will meet in gender concordant groups in a private room within their experimental clinic site; members will provide input on cultural factors that influence attitudes, perceptions, and beliefs about EIMC among pregnant couples.

They will provide guidance on cultural attitudes, ethnic preferences, beliefs and perceptions surrounding EIMC among pregnant couples in Lusaka. FGD members will inform the study on local issues or community concerns that could influence program uptake. No personal, individually identifying information will be collected and no individual interviews or assessments will be conducted with FGD members.

Couples Assessments.

Assessments at baseline will be completed using audio computer-assisted self-interview (ACASI) software, with support from study staff as needed. Participants will be assessed individually in a private office in the CHC; ACASI headphones and touchscreen computers will provide confidentiality and privacy. LFLS session 2 will be scheduled to coincide with the post-partum neonatal clinic visit in the first week following birth.

Each assessment measure (see attachment) is related to the study theoretical model, outcomes (feasibility, acceptability, uptake) and associated factors (e.g., plans, knowledge, norms, attitudes/beliefs and cultural or religious values associated with EIMC/VMMC, family decision making, stage of readiness).

After each LFLS session, a brief paper-based questionnaire will be individually administered to assess Stage of Change. VMMC/EIMC uptake and the role of parents, family members, peers and HIV serostatus in decision-making will be assessed by telephone or office visit at 6 months post-partum.

Couples intervention.

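### The timeline table stops the 6-month post-partum uptake assessment at M28-30, but enrolment to M24 puts the last of these visits at M33 to M36

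*Combined protocol and SAP*

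**What the plan says.** The text of section 10 sets the enrolment window: "Enrollment will be conducted from month 7 – 24, a total of 18 months". For follow-up it says "All S&S+LFLS study participants will be followed from enrollment to six months post-partum", and it gives the longest involvement as "time of participation based on enrollment at ~3-4 months pregnant = 12 months". Section 7 admits women up to 6 months pregnant.

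The timeline table in section 10 uses quarterly columns from M1-3 to M34-36. Its relevant rows are marked as follows:

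- Recruitment of the 300 couples: M7-9 to M22-24, in agreement with the text.
- "Postpartum: LFLS Session 2 Postpartum Follow-up Assess": M10-12 to M25-27.
- "6 mos post-partum: Assess EIMC/VMMC (father, sons, infant)": M16-18 to M28-30, then blank.
- "Data Analysis. Manuscripts. Prepare R01 application": M31-33 and M34-36.

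Section 12 (Couples Assessments) ties the second session to birth: "LFLS session 2 will be scheduled to coincide with the post-partum neonatal clinic visit in the first week following birth". The same section says that VMMC/EIMC uptake "will be assessed by telephone or office visit at 6 months post-partum". Section 11 lists EIMC uptake by the infant, and VMMC uptake by the father and other sons, as the primary endpoints.

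**The concern.** The text and the table cannot both be carried out. A couple enrolled in the last month of recruitment cannot reach six months post-partum by M30 at any eligible gestation, barring a very early birth. The table also fails on its own terms, because the 6-month row starts six months after the second-session row starts but ends only three months after it ends.

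This schedule governs when couple-level uptake is collected and when analysis begins. If staffing, budget and data lock follow the table, the couples enrolled last have no scheduled outcome contact, and the number of couples with male infants and a 6-month outcome falls below the planned 140 before any pregnancy loss or drop-out.

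**Working it through.** **Inputs.** Enrolment M7 to M24 and the 12-month maximum (section 10 text); eligibility up to 6 months pregnant (section 7); row marks (section 10 table); 300 couples, about 151 with male infants, 140 needed for 80% power, a 6-point difference (section 14, Power); 5% anticipated in the observation group (section 14, H3). Pregnancy is taken as 9 months, which the plan's own maximum implies: (9 − 3) + 6 = 12.

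**Plan figures that reproduce.** Enrolment: 24 − 7 + 1 = 18 months. Start of the 6-month row: enrol in M7 at 6 months pregnant, birth in M10, visit in M16, which is the first marked quarter.

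**End of the 6-month row.** With g the months pregnant at enrolment, lag = (9 − g) + 6 and last visit = M24 + lag. For uniform accrual (the documents give no accrual curve), count the enrolment months m = 7 to 24 with m + lag > 30.

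| g | Lag (months) | Last visit | Share due after M30 |
|---|---|---|---|
| 6 | 9 | M33 | 3/18 = 17% |
| 5 | 10 | M34 | 4/18 = 22% |
| 4 | 11 | M35 | 5/18 = 28% |
| 3 | 12 | M36 | 6/18 = 33% |

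Counting from the start of M24 rather than its end moves each last visit one month earlier, to M32-M35, still after M30. For every visit to fall by M30, enrolment would have to end between M30 − 9 = M21 (all at 6 months pregnant) and M30 − 12 = M18 (all at 3 months).

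**Check within the table alone.** Session 2 in M25-27 marks births in those months. Adding 6 months gives M31-33, where the 6-month row is blank. This needs no assumption about accrual or gestation.

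**Session 2 row.** Birth month is m + (9 − g). The share of births after M27, the row's last mark, is 0/18, 1/18, 2/18 and 3/18 (0%, 6%, 11%, 17%) for g = 6, 5, 4 and 3. Couples enrolled in M24 at 5, 4 or 3 months pregnant deliver in M28, M29 or M30.

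**Effect on numbers and power if the table is followed.** Outcomes available = 151 × (1 − share). One-sample normal power, two-sided 0.05, p0 = 0.05, p1 = 0.11:

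power = Φ{[0.06 − 1.96·√(0.05·0.95/n)] / √(0.11·0.89/n)}

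| Case | Share lost | n | Power |
|---|---|---|---|
| Planned | – | 140 | 82% |
| All enrol at 6 months | 17% | 126 | 78% |
| Gestation even over 3-6 months | 25% | 113 | 75% |
| All enrol at 3 months | 33% | 101 | 71% |

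The n = 140 result agrees with the plan's claim of at least 80%. By this formula 80% power needs 133.

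**The case against.** The strongest reply is that the harm is conditional and the power figures describe the wrong endpoint. No rule drops late couples, the text follows all of them, and visits at M33 to M36 still fit inside the 36-month study. EIMC is defined in section 6 as done within the first 60 days, so it could be ascertained early. Taking 60 days as two months, that window closes after M30 for only 0/18, 0/18, 1/18 and 2/18 of enrolment months (6, 5, 4 and 3 months pregnant). That leaves at least 151 × 16/18 ≈ 134 couples, just above the 133 needed. Hypothesis 3 is stated at clinic level, and the monthly clinic counts run to M30 without depending on the couple visit. Section 14 gives no VMMC test or power target. The H3 paragraph names a one-sample test while the power paragraph speaks of two conditions, so the power model used here is a choice. The 17% is a minimum only under uniform accrual; front-loaded recruitment would lower it.

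Most of this stands as a limit on size. It does not remove the conflict. The 6-month contact is the only one at which the plan schedules couple-level uptake to be recorded; an earlier EIMC check is possible but not planned. VMMC uptake by fathers and other sons remains open until that contact and cannot be read off at 60 days.

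Some merged rows of the table may not have extracted cleanly. The recruitment, Session 2 and 6-month rows each show all 12 columns, however, and recruitment matches the text. The M31-36 analysis marks and the M30 end of clinic data collection also fit a planned end of data collection at M30.

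**Conclusion.** The concern holds. The last 6-month visits fall at M33 to M36, three to six months after the row ends; the end of that row cannot be reproduced at any eligible gestation, and the table contradicts its own Session 2 row. The M33 figure assumes term birth. Enrolment before 3 months of pregnancy would run past M36, and preterm birth would bring a visit forward.

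The loss of outcomes arises only if the table is followed over the text. Under uniform accrual it would then be 50 to 100 of 300 couples, with the upper figure reached only if all enrol at 3 months pregnant. The EIMC power loss (to between 78% and 71%) further assumes that EIMC is recorded only at 6 months. VMMC uptake is the firmer loss, though the plan offers no power target against which to size it. If the text is followed instead, the consequence is that analysis is scheduled from M31 while primary-endpoint visits are still due. This should be corrected; it does not invalidate the design.

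**What to change.** Reconcile the table with the text of section 10:

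1. Extend the 6-month assessment row through M33, and to M36 for couples enrolled earlier in pregnancy.
2. Extend the Session 2 and post-partum follow-up row to about M30.
3. Add a sentence that couple-level uptake data are locked only after the last 6-month visit. Data cleaning, qualitative work and clinic-level analysis can still start at M31.
4. Optionally, record EIMC status by telephone at or after 60 days for late births, so that the EIMC analysis need not wait for the 6-month contact.

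The cost is two table rows and one sentence, and the 6-month contact may already be made by telephone. The drawback is that the final couple-level analysis is squeezed into the last months of the study or runs slightly past M36. The optional call adds one contact for late births and needs a protocol line. Closing enrolment early, at M21 to M18, would also reconcile the documents, but at a uniform rate it gives up 3 to 6 of the 18 enrolment months and so puts the planned 300 couples at risk.
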